3. OVERALL STUDY DESIGN AND PLAN

3.1. Overview

This is a multi-center trial, to be conducted at up to 30 sites in the United States, Canada, and Europe.

Inclusion criteria for participation in the trial include the presence of documented diabetes (Type I or II) with non-healing, full-thickness, University of Texas Classification of Diabetic Foot Ulcers Grade 1 and 2 diabetic foot ulcers of at least 4 weeks duration, but not greater than 1 year, measuring 1cm² or greater and less than or equal to 20 cm².

Subjects will be asked to sign a written informed consent form, approved by an IRB/Ethics Committee, prior to participation in the trial at the screening study visit. Each subject will be assigned a Subject Identification Number, which will be used for identification purposes in order to ensure subject confidentiality. All subject data held on the study Sponsor's database will be anonymised and identifiable only by Subject Identification Number.

Those who continue to meet all of the eligibility criteria after the 2 week run-in period will be enrolled into the trial and randomized to one of two treatment arms: TWO₂ therapy or, Control therapy.

In this trial a maximum of 220 subjects will be recruited. A Group Sequential Designs (GSD) with interims analyses after one third and two third recruited subjects has been chosen that will allow the trial to be stopped if TWO₂ therapy is obviously better than control therapy.

Subjects will be recruited as outpatients in participating wound care centers and clinics. At the screening visit the informed consent document must be signed, the wound will be measured and the subject will receive a standardized off-loading device for weight bearing wounds. The subject will from then on, be treated with predefined dressings used in the total treatment phase of the study.

A diary card will be given to every subject. Subjects will be instructed on keeping the simple diary card to record the use of the TWO₂ or control device, dressing changes and to collect data for health economic analysis. A study ID card will also function as an alert to other providers of participation in a clinical study (example Appendix I).

After a run-in period of 2 weeks the subject will be randomized into the study if the wound-size reduction is less than 30% of the initial measurement and all other inclusion and exclusion criteria are met.

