All subjects will receive 90 minutes of either TWO₂ therapy or control therapy at their home or nursing care facility 5 times a week for the treatment phase of up to 12 weeks. To secure double blinding no TWO₂ treatment will be done at the study centers. Delivery, installation and training on use of the TWO₂ device or control device may differ according to geographical location and shall be performed by trained accredited home health service providers utilizing nurses or other registered healthcare providers, or by trained home/durable medical equipment (DME) providers and an expert on the TWO₂ device or control device. The subject, or in some cases caregiver or healthcare professional (such as a home health nurse or aide), applying the TWO₂ therapy or control therapy will be adequately trained and assessed for competency on the use of the device, which will be reviewed monthly. Dressing changes at home (or equivalent) may be performed either by the subject, caregiver or healthcare professional such as a home health nurse or aide. Both the TWO₂ therapy and control therapy groups will visit the study center once per week for on

treatment study visits. Dressings will be pre-specified advanced moist wound therapy (AMWT) dressings, which will be changed at a minimum of once weekly according to the PI/Subl Investigator's (Subl) clinical judgment. Subjects will receive standardized off-loading for a weight bearing wounds or an open heel boot for posterior heel wounds. A Charcot Restraint Orthotic Walker boot (CROW boot) may be used where there is a need to protect a Charcot Foot deformity. Debridement will be performed as needed according to the PI/Subl clinical judgment.

The treatment phase of the study will be 12 weeks. At every on treatment study visit at the clinic, foot ulcers are photographed. The initial (baseline) measurement after debridement will serve as the standard. Digital images will be sent to a blinded central assessor to be assessed and measured.

Once wounds are initially considered closed, that visit will serve as the first of two confirmatory visit. All subjects will continue treatment for an additional 2 weeks, to confirm wound closure.²³ During this period, subjects will continue to receive TWO2 therapy or Control therapy, use and change dressings, and use the off-loading device, where it is required, per the protocol. For subjects whose wounds close at week 11 or later the treatment phase will continue to the second confirmatory visit.

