6.3.1. Debridement

Adequate debridement is key for wound healing in diabetic ulcers. All wounds will receive baseline sharps debridement of all callus/necrotic tissue and additional debridement as needed throughout the trial. Debridement will be performed where it is determined to be clinically necessary by the PI/SubI.

Any surgical debridement has to be documented on CRFs, reported as an adverse event and will be included in analysis of product safety and efficacy.

Standardized debridement will be part of the Investigators training. To ensure the same standard of debridement/wound preparation in all centers, photographs of all subjects will be evaluated by a central assessor.

Enzymatic debridement products, like other concomitant topical products, can confound results in topical wound-treatment product trials and therefore must be prohibited.

6.3.2. **Off-Loading**

Excessive pressure on the sole of the foot is one of the key factors in the pathogenesis of neuropathic plantar ulcers. Consequently pressure relief is of fundamental importance in the treatment of the diabetic foot ulcer³⁰ and has been intensively proven in well designed randomized clinical trials.^{24,26,31,32}

Therefore all subjects in the present study will be provided with an off-loading device (for weight bearing wounds) from Salvatelli srl, Italy (Piaggesi study):

During the weekly wound assessment, subjects will be educated about the importance of the off-loading (where it is required).

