8. TRIAL CONDUCT

8.1.1. Overview of Screening Treatment and Follow-Up Requirements

Procedure / Examination	Screening & Start Run-In	Baseline * (2 weeks later)	1	2	3	4	5	6	7	8	9	10	11	12	12 wks Follow up	38 wks Follow up
Informed Consent	X															
In-& Exclusion criteria	X	X														
Randomization		X														
Adverse Effects and Events		X	X	X	X	X	X	X	X	X	X	X	X	X	X	X
Medical History/ Preexisting Conditions	X															
Record Concomitant Medications	X	X	X	X	X	X	X	X	X	X	X	X	X	X	X	X
Compliance assessment (treatment, dressings)		X	X	X	X	X	X	X	X	X	X	X	X	X		
Height and Weight	X															
Wound History (Duration; course of healing last 12 months and previous treatment modalities)		X														
Dressing removal / wound cleansing and re-dressing	X	X	X	X	X	X	X	X	X	X	X	X	X	X		
Wound assessment and measurement (location, size)**	X	X	X	X	X	X	X	X	X	X	X	X	X	X		
Pain assessment	X	X	X	X	X	X	X	X	X	X	X	X	X	X	X	X
Neuropathic assessment	X															
Infection Assessment	X	X	X	X	X	X	X	X	X	X	X	X	X	X		
ABI and Secondary Vascular Assessment ***	X															
Dig. Photographs (post debridement)	X	X	X	X	X	X	X	X	X	X	X	X	X	X	X	X
Debridement if needed		X	X	X	X	X	X	X	X	X	X	X	X	X		
Cardiff Wound Impact Schedule ****	X	X													X	X
Lab tests	X														X	
Punch biopsies *****		X				X										
Education on diabetic foot care/off-loading*****	X	X	X	X	X	X	X	X	X	X	X	X	X	X	X	X
Economic assessment		X				X				X				X	X	X
Device competency assessment		X				X				X						

Note: *Baseline visit window is -1/+2 days. All follow-up visit windows are +/- 2 days. 12 and 38 Week follow-up +/- 2 weeks

** Measurement recorded from central assessor report plus manual measurement at baseline

*** Secondary vascular testing only needed if not within 4 months of screening date

**** Cardiff Wound Impact Schedule (debriefing of subjects week 38 Follow up where not previously validated)

***** Optional (none for sub-study)

***** Off-loading with study boot or CROW boot where required

***** Health Economic Assessment (EQ-5D, dressing history up to 8 weeks and significant related medical events)

8.1.2. **Wound Closure Assessment**

Procedure / Examination	Wound Closure Visit # 1	Wound Closure Visit # 2
Verify Informed Consent	X	X
Adverse Events	X	X
Record Concomitant Medications	X	X
Compliance assessment (treatment, dressings)	X	X
Confirm Wound Closure Assessment	X	X
Dressing removal / wound cleansing and re-dressing	X	
Pain assessment	X	X

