9 STATISTICAL ANALYSIS

9.1 Sample Size and Power Analysis

All sample size estimations in this section of the protocol were undertaken using the sampsi function in Stata 11 (Statcorp LP, Texas, USA). Comparisons of groups was made assuming no continuity correction.

Little data are available on similar studies using topical oxygen therapy within randomized clinical trials making sample size estimation problematic. Large trials of dermal substitutes and negative pressure have been undertaken that can be used to indicate the potential healing in the control group. The three large trials have control healing of between 18% and 28.9% around 12 weeks after entering the trial, with a mean of 28%.^{25,27,29}

The expected improvement in healing using the active device is more problematic as there have been few comparative studies published. Aburto and Frye undertook a randomized study of 20 venous ulcers and 20 diabetic foot ulcer patients.⁴² Topical oxygen demonstrated higher healing in the DFU patients after 90 days of 90% versus 40% in the control group. Blackman et al randomized 28 patients with DFUs and obtained a similar response (82.4% versus 45.5%).²² The potential difference between treatment groups was therefore 50% and 36.9% respectively. Using these studies a total sample size of 28 and 52 would be expected based on 80% power at the 5% level of significance. Neither of these studies was blinded. It is therefore likely that the effect is likely to be substantially smaller than that experienced in these two studies.

Because of the small size of these trials and lack of blinding it has been decided to offer a more cautious approach to the calculation of sample size based on a smaller expected benefit of oxygen therapy. By combining the results of the two randomized studies already undertaken the control group achieved a healing rate of 9/21 (42.8%). In the actively treated group healing occurred in 23/27 (85.2%). Assuming an expected control rate of 43% and a difference of half that experienced in these trials of 21% (to 64%) would require a sample size of 88 patients in each group (total=176), with a power of 80% and a level of significance set at $p<0.05$.

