In order to overcome the uncertainty surrounding the expected benefit, the trial will be undertaken using group sequential design (GSD) allowing for interim analysis to be performed at intervals during the trial recruitment. The interim analysis will take place after one third of subjects have been recruited, after two thirds and then a final analysis at full recruitment. The Pocock method of interim analysis will be used, which requires an equal level of significance ($p<0.022$) over the three analyses.⁴³ If the difference in primary outcome produces a probability less than this in any of the analyses then the null hypothesis is rejected and the alternative hypothesis of a difference in healing has been shown. In order to achieve this level of significance a total of 110 patients need to be recruited to each arm of the trial (total=220).

Since all patients will achieve a 12 week end point (healed versus unhealed) no uprating of this sample size will be made to take into consideration patients lost to follow up (see section 9.2).

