9.3 Primary outcome analysis

The primary endpoint is the “Incidence of complete wound closure within 12 weeks”.

The null hypothesis to be tested is that there is no difference between treatment groups in terms of the rate of wound healing after 12 weeks of study treatment. The alternative hypothesis is that such a difference exists.

Uncorrected Chi squared analyses will be used to determine the difference between treatment groups in terms of wound closure rate within 12 weeks, at the interim analysis. 95% confidence intervals will be estimated using the normal approximation interval.

Logistic regression analysis will be used to determine the effects of confounding on the primary outcome at the trial end. In particular, gender, age, ulcer duration, size and diabetic factors will be considered in the model. A stepwise procedure will be used to eliminate non-significant covariates from the model. The effect of different centers' outcomes will be entered as a random effect into the model.

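### The final logistic model in Section 9.3 names neither ulcer site nor run-in wound change, so a modest precision gain and a pre-specified correction of chance imbalance are forgone

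*Combined protocol and SAP*

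**What the plan says.** **Site and co-treatment.** Section 3.1 ties off-loading to ulcer position: "Subjects will receive standardized off-loading for a weight bearing wounds or an open heel boot for posterior heel wounds". It also allows a CROW boot for Charcot deformity. Section 6.3.2 gives the reason: "pressure relief is of fundamental importance in the treatment of the diabetic foot ulcer".

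**Run-in change and entry.** Section 3.1 says "the subject will be randomized into the study if the wound-size reduction is less than 30% of the initial measurement", and Section 4.1 repeats the limit as an inclusion criterion.

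**Data available before randomization.** The schedule in Section 8.1.1 has the row "Wound assessment and measurement (location, size" ticked at both screening and baseline. Sections 8.2.1 and 8.2.2 list location, size and a post-debridement photograph at both visits.

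**Randomization.** Section 5 describes permuted blocks and states no stratification factor.

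**Analysis.** Section 9.3 gives an uncorrected chi-square test for the interim analysis and a logistic regression at trial end. On covariates it says "In particular, gender, age, ulcer duration, size and diabetic factors will be considered in the model". A stepwise procedure then removes non-significant ones, and center enters as a random effect. Section 9.1 sets the Pocock rule, "which requires an equal level of significance ($p<0.022$) over the three analyses". Section 9.6 puts the interim looks at 73 and 146 subjects.

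**The concern.** The plan already accepts covariate adjustment at trial end. The list it names leaves out two baseline facts that the design itself singles out, one because it selects the off-loading and the other because it selects the subjects. An ulcer that shrank 29% in the run-in and one that grew are both eligible, and nothing in the named model separates them. The same is true of a weight-bearing and a non-weight-bearing ulcer.

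If either variable predicts closure, two things are at stake. Precision that costs no extra visit is left unused. And a chance difference between arms in site mix or prior healing enters the estimated closure difference, with no correction fixed in advance. Deciding on such an adjustment after seeing the data would be open to challenge, and stepwise selection makes its presence in the final model depend on the data.

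**Working it through.** **1. Reproduce the plan's sample size.** Inputs from Section 9.1: 43% against 64%, 80% power, no continuity correction. The test is two-sided, inferred from Section 9.3: "The alternative hypothesis is that such a difference exists".

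n per arm = [z(1−α/2)·√(2·p̄·q̄) + z(0.80)·√(p₁q₁ + p₂q₂)]² / d²

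Here p̄ = 0.535, q̄ = 0.465, d = 0.21, √(2·0.535·0.465) = 0.7054 and √(0.2451 + 0.2304) = 0.6896.

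- α = 0.05: (1.960·0.7054 + 0.8416·0.6896)² / 0.0441 = 87.4, so 88. This matches.
- α = 0.022: (2.290·0.7054 + 0.8416·0.6896)² / 0.0441 = 109.3, so 110. This matches.

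Power at 110 per arm and α = 0.022 is 80.3% at the final look taken alone. Over looks at 73, 146 and 220 the normal approximation gives overall power of about 83% and overall two-sided error of 0.0496. No covariate enters these figures, so omitting covariates does not reduce them.

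**2. Possible gain, by approximation.** If the two covariates explain a fraction R² of the closure variance (assumed), effective n is about 110/(1−R²).

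| R² | Final-look power | n per arm for 80% |
|---|---|---|
| 0 | 80.3% | 110 |
| 0.02 | 81.2% | 108 |
| 0.05 | 82.5% | 105 |
| 0.10 | 84.7% | 99 |
| 0.15 | 86.9% | 94 |

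**3. Possible gain, by simulation.** Marginal rates were held at 43% and 64%. Odds ratios are assumed (site, then run-in change per SD).

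*Final look only, 4,000 trials per scenario, 50% weight-bearing, chi-square against adjusted Wald:*
- 1 and 1: 82.2% against 80.3%
- 1.5 and 1.25: 82.0% against 80.6%
- 2 and 1.5: 82.0% against 82.9%
- 3 and 2: 82.2% against 86.5%

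*Three looks, 3,000 trials per scenario, 60% weight-bearing, chi-square against adjusted likelihood-ratio at every look:*
- 1 and 1: 85.3% against 84.5%
- 1.5 and 1.5: 85.0% against 85.9%
- 2 and 2: 84.5% against 87.3%
- 3 and 2: 84.6% against 88.4%

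The gain runs from nil or slightly negative at weak effects to about 4 points at strong ones. With baseline size already in the model, adding both variables gave 86.2% to 88.2% at odds ratios of 1.5 and 1.5, 85.9% to 89.6% at 2 and 2, and 85.6% to 92.0% at 3 and 2.5. That last gain, 6.4 points, comes from the most favorable assumptions and from adjusting at every look, which step 5 shows to be liberal.

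**4. Chance imbalance.** For a binary site with prevalence p, the SD of the between-arm difference is √(4p(1−p)/N). At p = 0.5 (assumed):
- N = 73: SD 11.7 points, 95% range ±22.9, 39% chance of exceeding 10 points
- N = 146: SD 8.3 points, ±16.2, 23%
- N = 220: SD 6.7 points, ±13.2, 14%

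Shift in the estimate = imbalance × closure difference between sites. A 10-point imbalance with an assumed site difference of 10 to 30 points shifts it by 1 to 3 points, against a planned difference of 21.

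**5. At which look to adjust.** Under the null with odds ratios of 2, the adjusted likelihood-ratio test at 73 subjects rejected in 0.028 of trials against a nominal 0.022. Used at all three looks it gave an overall error of 0.060. Chi-square at the two interims with the adjusted model only at the final look gave 0.049 to 0.051 and kept nearly all the gain. The random center effect of Section 9.3 is not in these simulations.

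**The case against.** The strongest reply is that nothing in the plan is wrong. The sample size is unadjusted and reproduces, and power exceeds 80% without these covariates. Chance imbalance is not bias, because the variance of the chi-square test already allows for it. All of that stands. A reader might infer that the trial loses planned power or that its error rate is unprotected; the figures in steps 1 and 5 do not support either.

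A reader might also infer that the protocol calls these variables strongly prognostic. It does not. Section 6.3.2 stresses pressure relief as a treatment and does not say that site predicts closure once off-loading is given. Sections 3.1 and 4.1 use run-in change only as an entry filter. That filter removes the fastest healers and so may weaken the variable.

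Nor are the two variables excluded at the final analysis. The wording of 9.3 leaves its list open, and 9.4.1 lets any factor thought important be tested in the Cox model. They are permitted but not pre-specified, and stepwise selection can remove them.

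Two practical objections also hold. The plan records location, not weight-bearing status, so a derivation rule is needed. And finer versions ask for more than the plan supplies: with an assumed 10% of posterior heel ulcers, a three-level site had a heel category with all or no closures in about 6% of simulated first looks, and the linear measure of 9.4.2 needs perimeters at screening, whereas 7.1.1 specifies circumference at baseline. This is why the fix uses a binary site and percent area change.

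**Conclusion.** The point holds in a limited form. Section 9.3 commits to adjustment at trial end, yet leaves out two baseline variables that the design itself uses and exposes any covariate to stepwise removal. The cost is a forgone gain, not a flaw in the planned power or type I error: about 1 to 5 power points if the variables are moderately to strongly prognostic, and a loss of about 1 point if they are not (0.8 by likelihood ratio over three looks, 1.9 by Wald at the final look). A correction of chance imbalance fixed in advance is also missing.

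The size rests wholly on assumed odds ratios and site prevalence. Imbalance is largest at 73 subjects, and it is tempting to conclude that the interim tests should be adjusted too. The simulated error rates speak against that, so the interim looks are better left unadjusted.

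**What to change.** In Section 9.3, pre-specify two fixed covariates in the final logistic model, exempt from stepwise elimination:

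1. Weight-bearing site, yes or no, derived from the recorded baseline location by a written rule fixed before unblinding.
2. Percent change in wound area from screening to baseline, which the eligibility check already requires.

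State that this model gives the final-look decision at p<0.022, since 9.3 does not now say whether the chi-square or the regression decides there. Keep the uncorrected chi-square at 73 and 146 subjects. Report a standardized risk difference beside the odds ratio. Use the same two covariates in the Cox model of 9.4.1, also exempt from elimination.

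The cost is analysis-plan wording, one mapping rule, one derived variable, two degrees of freedom, and a conditional odds ratio, which the standardized risk difference offsets. No visit, procedure or subject is added. Before adoption, the error rate of the final model should be checked by simulation with the random center effect included.

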3.2. Flowchart of Subject Flow

3.3. Endpoints

3.3.1. Primary Study Endpoints

The primary endpoint is the:

Incidence of complete wound closure within 12 weeks.

Closure is defined as 100% skin re-epithelialization without dressing requirements which is confirmed by 2 consecutive study visits 2 weeks apart.

3.3.2. Secondary Study Endpoints

1. Time to complete wound closure
2. Change in wound size over time
3. Incidence of reoccurrence
4. Incidence of amputation
5. Incidence of adverse events
6. Quality of Life – Pain, Mood and Function
7. Health Economic Analysis

3.3.3. Safety Endpoints

Incidence, duration and severity of adverse events and device effects will be documented in every case. This includes:

- Incidence of severe infections needing hospitalization
- Malfunctioning of the device
- Worsening of the wound
- Death

3.3.4. ***Justification for Trial Design***

The choice of using the “Incidence of complete wound closure” as the primary endpoint is in accordance with the recommendation of the FDA document “*Guidance for Industry, Chronic Cutaneous Ulcer and Burn Wounds, Developing Products for Treatment*”.²³

The choice of the parallel group design is the most appropriate for a wound healing study.

The treatment duration of 12 to 16 weeks is a standard in randomized clinical trials in wound care.²⁴⁻²⁹ Two recent studies with the TWO₂ system in venous and diabetic ulcers showed that the majority of ulcers treated with topical oxygen show wound closure after 12 weeks.^{21,22}

A double blind trial is the gold standard in trial design.

Although there are a number of published reports reporting positive results on topical oxygen treatment and diabetic foot ulcers there is no comparative trial so far. In order to overcome the uncertainty surrounding the expected benefit, the trial will be undertaken using group sequential design (GSD) allowing for interim analysis to be performed at intervals during the trial recruitment.

For the purposes of standardizing to reduce treatment variability the choice of dressings for this trial will be specifically limited.

All “active” dressings will be excluded from the trial. These include: antimicrobial dressings containing silver, iodine or Polyhexamethylene Biguanide (PHMB), dressings containing enzymes, and growth factors (Regranex® or dermal skin substitutes like Apligraf® or Dermagraft®).

Adjunctive treatments such as Hyperbaric oxygen therapy (HBO), Vacuum assisted closure (VAC), Heat therapy, Laser Therapy, Mechanical constant tension, Larval/maggot therapy (Biodebridement), Artificial Skin and Electrical stimulation for Tissue Repair (ESTR) are not allowed in this study.

No local antimicrobial treatments are allowed in the study. Systemic antibiotic treatment of infection will be prescribed according to local standards.

Histological studies in pigs treated with topical oxygen showed signs of improved angiogenesis and tissue oxygenation. Immunohistochemical analyses revealed a stronger presence of Vascular Endothelial Growth Factor (VEGF) in the tissue from oxygen treated wounds in pigs compared to the non-treated controls.¹⁷ As no studies have investigated these effects in humans, punch biopsies from 20 randomized subjects may be planned at selected centers and taken at baseline and after 4 weeks.

Recent RCTs with patients with diabetic foot ulcers from Blume et al., 2008 investigating Negative Pressure Wound Therapy versus advanced Moist Wound Therapy and the paper from Löndahl, 2010 where Hyperbaric Oxygen Therapy was evaluated as an adjunctive therapy did not exclude infected ulcers. As oxygen is critical to fight infection in chronic wounds³³⁻³⁵ and the TWO₂ device has been shown to eliminate infections and multi-resistant staphylococcus aureus (MRSA)^{21,22,36}, in this trial wound infections will not be excluded. However, any subject with wound infection must be under treatment at the time of randomization.

